### Research objectives

The specific objectives of this study are:

1. To estimate the overall and annual prevalence of immunoglobulin use in the general population, overall and stratified by i) type of immunoglobulin, and ii) route of administration. Estimates will be stratified by age and sex.
2. To describe the distribution and quarterly trends of prespecified immunoglobulin brands among prevalent immunoglobulin users (if available).
3. To estimate the number of immunoglobulin prescriptions, treatment duration, and dose (initial, cumulative) of immunoglobulin use during the study period.
4. To characterise patients initiating treatment with prespecified immunoglobulins in terms of i) demographics at index date, ii) indication for use, iii) comorbidities, iv) common infections post-index, and v) antibiotics post-index.

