## 8.2. Follow-up

For prevalence estimations of individuals with recorded immunoglobulin prescriptions among the general study population (*objective 1*), individuals present in the data source between 1st of January 2017 and 31st of December 2024 will be included. For prevalence estimations among immunoglobulin users (*objective 2*), follow up will start on date of immunoglobulin prescription during the study period.

For patient-level drug utilisation (*objective 3*) and characterisation of individuals initiating immunoglobulin treatment (*objective 4*), follow-up of incident immunoglobulin users will start on the date of the first immunoglobulin prescription record of prespecified immunoglobulin brands during the study period. For primary care data sources, individuals are required to have 180 days data visibility prior to study inclusion and should not have a record of immunoglobulin prescription in the 180 days prior to study inclusion. For hospital care data settings, individuals are not required to have prior data availability, and no washout period will be applied prior to study inclusion. To ensure sufficient follow-up (*objectives 3–4*), only individuals with a first record of immunoglobulin prescription at least 180 days before the end of data availability in each data source will be included.

Follow-up (*objectives 1–4*) will end on the earliest of i) loss to follow-up, ii) death, iii) end of observation period (the latest available data), iv) or study end date 31/12/2024, whichever occurs first.

The code lists used to identify the start and end of follow-up determining events are presented in [Annex IV](#).

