## 8.7. Study size

No sample size has been calculated, as this is a characterisation and drug utilisation study with a descriptive design, which will not test a specific hypothesis. In addition, we will use already available data to describe treatment and characteristics of individuals receiving immunoglobulins. Thus, the sample size is driven by the availability of data for individuals with a prescription for prespecified immunoglobulin types and brands. Based on a preliminary feasibility assessment, the expected number of person counts for immunoglobulins in the data sources included in this study range from 10,900 (CDW Bordeaux) to 73,600 (CPRD GOLD).

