#### Drug exposure calculations

Drug eras are defined as follows: exposure starts at the date of the first prescription of prespecified immunoglobulin brand during the study period. For primary care data sources, a washout period of 180 days will be applied prior to inclusion. For each prescription, the estimated duration of use will be retrieved from the drug exposure table in the OMOP CDM, using the recorded start and end date of the exposure. Subsequent prescriptions will be combined into continuous exposed treatment episodes (drug eras) using the following specifications: two drug eras will be merged into one continuous drug era if the distance in days between end of the first era and start of the second era is  $\leq 30$  days. The time between the two joined eras will be considered as exposed by the first era as shown in **Figure 4**, first row. The cumulative dose is the sum of defined daily doses (DDDs) multiplied by the number of days exposed to each dose, i.e., the total dose taken throughout the exposures considered in the time-window reported per prespecified immunoglobulin brand.

Gap era joint mode	Schematics	Dose in between	Cumulative dose	Cumulative time
"first"		$d_1$	$d_1 \cdot (x_1 + x_{12}) + d_2 \cdot x_2$	$x_1 + x_{12} + x_2$
"second"		$d_2$	$d_1 \cdot x_1 + d_2 \cdot (x_2 + x_{12})$	$x_1 + x_{12} + x_2$
"zero"		0	$d_1 \cdot x_1 + d_2 \cdot x_2$	$x_1 + x_{12} + x_2$
"join"	 <small>first exposure      gap      second exposure</small> <small>time = <math>x_1</math>, dose = <math>d_1</math>      time = <math>x_{12}</math>      time = <math>x_2</math>, dose = <math>d_2</math></small>	NA	$d_1 \cdot x_1 + d_2 \cdot x_2$	$x_1 + x_2$

Figure 4. Gap era joint mode.

If two exposures overlap, the overlap time will be considered exposed to the first exposure (**Figure 5**). No time will be added at the end of the combined drug era to account for the overlap. If two exposures start at the same date, the overlapping period will be considered exposed to both.

Overlap mode	Schematics	Dose overlap
"first"		$d_1$
"second"		$d_2$
"both"		$d_1 + d_2$
"maximum"		$\max(d_1, d_2)$

Figure 5. Gap era overlap mode.

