The number of prescriptions, initial and cumulative dose of the index drug, as well as duration of use, will be provided per prespecified immunoglobulin brand as minimum, q25, median, q75, and maximum. For data sources where duration cannot be calculated, due to e.g., missing information on quantity or dosing, treatment duration will not be provided.

### Objective 4

Characteristics of individuals will be assessed in predefined time windows around the date of the first recorded prescription of immunoglobulins (index date) during the study period. For primary care data sources, a washout period of 180 days will be applied. Characteristics will be described for each prespecified immunoglobulin brand by means of large-scale characterisation and prespecified patient-level characteristics based on OMOP CDM mapped data using the *CohortCharacteristics* (<https://github.com/darwin-eu/CohortCharacteristics>) and *DrugUtilisation* (<https://github.com/darwin-eu/DrugUtilisation>) R packages, developed by DARWIN EU®.

Characteristics of interest will be reported as counts and proportions for categorical variables and as minimum, q25, median, q75, and maximum for continuous variables. Demographic characteristics, including age and sex, will be assessed at the date of first recorded prescription of immunoglobulins (index date) during the study period. Characterisation of prespecified indications for use will be assessed any time prior to 7 days after the index date, 30 days prior to 7 days after the index date, and 7 days prior to 7 days after the index date. Large-scale characterisation of comorbidities prior to immunoglobulin treatment will be assessed 30 days prior to the index date, 1 year prior to the index date, and any time prior to the index date. Characterisation of prespecified common infections and prespecified antibiotics treatment among immunoglobulin initiators will be assessed up to 30 days post-index and up to 365 days post-index.

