#### **Germany: IQVIA Disease Analyzer Germany (IQVIA DA Germany)**

IQVIA DA Germany will be included in this study because it is a primary care data source that provides relevant information on the use of immunoglobulins in the general population.

Based on a preliminary feasibility assessment, the expected number of person counts for immunoglobulin use in IQVIA DA Germany will be 47,500.

Moreover, data availability and follow-up in IQVIA DA Germany is sufficient, as data availability starts in 1989, and the date of most recent data extraction 12/2024, which aligns with the study period. The median follow-up of the first observation period is 116 days.

There are no study specific limitations present in IQVIA DA Germany.

Lastly, IQVIA DA Germany requires no IRB approval, which makes the execution of this study feasible within the current study timelines.

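### Objective 3 totals (prescriptions, days exposed, cumulative dose) run over unequal follow-up, so differences between brands and sources in Table 3 partly reflect observed time

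*Protocol*

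**What the plan says.** The research objectives ask for number of prescriptions, duration and "dose (initial, cumulative) of immunoglobulin use during the study period". Under Drug exposure calculations (section 8.8.3) these "will be provided per prespecified immunoglobulin brand as minimum, q25, median, q75, and maximum"; the Table 3 shell in 8.8.4 adds a mean and sets the three sources in adjacent columns under each brand.

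Follow-up "will start on the date of the first immunoglobulin prescription record of prespecified immunoglobulin brands during the study period" (section 8.2). It ends at loss to follow-up, death, end of observation "or study end date 31/12/2024, whichever occurs first".

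Cumulative dose is defined as "the total dose taken throughout the exposures considered in the time-window reported per prespecified immunoglobulin brand", but no window length is given for objective 3. Objective 4, by contrast, has fixed post-index windows of [0, +30] and [0, +365] days for infections and antibiotics.

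The safeguard in 8.2 is that "only individuals with a first record of immunoglobulin prescription at least 180 days before the end of data availability" are included. The matching attrition row in Table 2 speaks of potential follow-up. Table 4 reports future observation by brand and source; Table 3 has no follow-up row.

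**The concern.** A count of records, a sum of exposed days and a summed dose keep rising for as long as a treated person is observed, and stop when observation stops. If treatment is still running then, the recorded total is a lower bound, yet it enters the quartiles as if complete. Two brands, or two sources, with the same true pattern of use can then show different medians because their users were watched for different lengths of time.

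The research question is about treatment characteristics across European countries, and Table 3 is laid out by brand and by source. A reader could take a higher median in one column for heavier or longer use. The limitations section mentions the differing definitions of observation period only for the prevalence population of objective 1.

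**Working it through.** There is no figure of the plan to reproduce: "No sample size has been calculated, as this is a characterisation and drug utilisation study with a descriptive design". The check is date arithmetic plus an illustration.

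**Calendar limits.** Inputs: study period 01/01/2017 to 31/12/2024 (8.5); source data end 09/2025, 12/2024 and 05/2025 (8.4 Table 1, Annex II). The day of the month is not given, so a range is shown.

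- Longest follow-up: 31/12/2024 − 01/01/2017 = 2,921 days.
- Last eligible index = min(31/12/2024, data end − 180 days).
- Shortest follow-up the calendar allows = min(31/12/2024, data end) − last eligible index.

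| Source | Last eligible index | Shortest follow-up |
|---|---|---|
| CDW Bordeaux | 31/12/2024 | 0 days |
| IQVIA DA Germany | 04/06 to 04/07/2024 | 180 days |
| CPRD GOLD | 02/11 to 02/12/2024 | 59 to 29 days |

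The rule therefore secures 180 calendar days inside the study period only in IQVIA DA Germany. In all three sources a person's own observation can end sooner through loss, death or last recorded contact.

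**Illustration of the mechanism.** These are assumptions, not document figures: identical use in every source; exponential treatment duration; one record every 28 days; uniform entry; exponential observation after index, with the sources' stated medians of 247, 116 and 2,150 days borrowed for it; cut-off at 31/12/2024; 400,000 simulated people per source. Raw medians, Bordeaux / IQVIA / CPRD GOLD:

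| True median duration | Days exposed | Records |
|---|---|---|
| 180 days | 99 / 71 / 155 | 4 / 3 / 6 |
| 365 days | 137 / 88 / 272 | 5 / 4 / 10 |
| 730 days | 169 / 100 / 428 | 7 / 4 / 16 |

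For brands within one source (study-end cut-off only, true median 730 days), assumed availability from 2017, 2020 or 2023 gives 569, 500 or 348 days and 21, 18 or 13 records.

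**What a common window does.** The median of a capped quantity is the capped median. Cutting the 730-day row at 180 days therefore gives 169 / 100 / 180 days. With at most 1 + floor(180/28) = 7 records, the counts become 7 / 4 / 7. The CPRD GOLD to IQVIA ratio in days falls from 428/100 = 4.3 to 180/100 = 1.8. The distortion shrinks but remains, because some people are not observed for the whole window. Among those observed for all 180 days the median is 7 records in every source, but they are only 57%, 34% and 89% of initiators. A Kaplan-Meier median recovers the true duration for the three rows (180; 363 to 366; 725 to 738 days), given that in this simulation the end of observation is unrelated to stopping treatment.

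**The case against.** The strongest reply is that objective 3 is descriptive. Total recorded use over a stated period is a legitimate quantity, no brand or source contrast is tested, and sources are not pooled (8.9). Table 4 already lets a careful reader see unequal observation by brand and source, and a window length might be left to a later analysis plan. This has weight: it limits the point to interpretation and presentation. It does not remove it, because the protocol itself fixes the period, the summary statistics and the table shell, and a row in another table corrects nothing in Table 3.

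Some stronger readings are tempting but not supported:

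- A reader might take 2,150/116 = 18.5 as the gap in follow-up between CPRD GOLD and IQVIA DA Germany. Annex II says "The median follow-up of the first observation period is 116 days" of the source as a whole. Initiators in the two primary care sources need 180 prior days, so a person whose only observation period lasts 116 days could not enter objective 3.
- A reader might quote a 16-fold range (2,921/180 = 16.2), or about 104 versus 6 records at one every 28 days. The 180-day floor fits only IQVIA DA Germany, and the record counts set calendar extremes against each other under assumed uninterrupted use. They say nothing about the reported medians.
- Nor do all totals grow with observed time. They stop growing for anyone who stops treatment. If only the first drug era is summarised, which the text does not settle, later time adds nothing, though a long era is still cut off.
- That brands used early look heavier than recent ones is an inference; the protocol gives no launch dates.

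**Conclusion.** The point holds in a limited form. Number of prescriptions, days exposed and cumulative dose are truncated for people still on treatment when observation ends, and the plan neither standardises the window nor accounts for that truncation. Differences in Table 3 therefore partly reflect observed time. Initial dose is not affected.

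The size cannot be read from the documents, since follow-up among initiators is not given. It is small for single or short courses and grows with long-term use; the simulated figures show mechanism and direction only. What is firm is that the 180-day rule does not do what it is meant to do: it leaves 0 days possible in CDW Bordeaux and 29 to 59 in CPRD GOLD before study end, and in every source it concerns potential, not observed, time.

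**What to change.** In 8.8.3 and the Table 3 shell:

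- Add a block giving the three quantities within a common post-index window, for example [0, +180] days, for all initiators, with the number observed for the whole window. Show the fully observed subset only as a sensitivity summary: where observation runs to the last event or visit, it keeps the people who came back.
- Measure the 180-day rule to the earlier of 31/12/2024 and the end of source data.
- Add observed time after index and the number still in a drug era at the end of observation.
- Give duration with a Kaplan-Meier median. Read it beside that number, because observation ending at the last contact may be related to stopping treatment.
- Keep the whole-period summary. Do not use individual per-person-year rates in IQVIA DA Germany or CDW Bordeaux, where someone with a single contact has almost no denominator.

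The cost is one more table block and a slightly smaller cohort. The last index date becomes 04/07/2024. Under uniform entry (an assumption) that removes about 180/2,921 = 6% of CDW Bordeaux initiators and 121/2,862 to 151/2,892 = 4% to 5% in CPRD GOLD. A fixed window also does not describe long-term use, which is why the whole-period summary should stay.

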### *Objectives 3–4*

For primary care data sources, the study population will include all individuals who initiate immunoglobulin treatment with prespecified immunoglobulin brands and are present in the data source during the study period. Individuals are required to have 180 days data visibility prior to study inclusion and should not have a record of an immunoglobulin prescription in the 180 days prior to study inclusion. To ensure sufficient follow-up time, only individuals who initiated immunoglobulin treatment at least 180 days before the end of the available data will be included.

For hospital care data settings, the study population will include all individuals who have an immunoglobulin record and are present in the data source during the study. Individuals are not required to have prior data availability, and no washout period will be applied prior to study inclusion. To ensure sufficient follow-up time, only individuals who initiated immunoglobulin treatment at least 180 days before the end of the available data will be included.

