#### *Objectives 3–4*

##### Inclusion criteria

- Present in the data source during the period of 01/01/2017 to 31/12/2024.
- Minimum 180 days of available history before index data. This criterion does not apply for hospital data source CDW Bordeaux.
- First drug prescription or dispensing record of prespecified immunoglobulin brand during the study period.
- No prior immunoglobulin exposure in the 180 days prior to the index date. This criterion does not apply for hospital data source CDW Bordeaux.

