##### Exclusion criteria

- Individuals with a first immunoglobulin record <180 days prior to the end of data availability in the respective data source (to ensure sufficient follow-up).

The preliminary code list for immunoglobulins brands is provided in [ANNEX IV](#).

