### 8.6.3. Covariates, including confounders, effect modifiers, and other variables

The variables for *objective 1* are as follows:

- Calendar period
  - Year
- Route of administration:
  - Intravenous
  - Subcutaneous
  - Intramuscular
  - Other
  - Missing
- Age groups, defined at cohort entry date:
  - Overall population
  - 1 to 18 years
  - 19 to 65 years
  - >65 years and older
- Sex, defined at cohort entry date:
  - Overall
  - Male
  - Female

The variables for *objective 2* are as follows:

- Calendar period
  - Quarter of year
- Prespecified brands, including (if available):
  - Flebogamma DIF
  - Kiovig
  - Privigen
  - Octagam (5% and 10%)
  - Yimmugo
  - Ig vena
  - Intratect
  - Iqymune
  - Panzyga/Globiga
  - Gamunex
  - Hizentra
  - Hyqvia
  - Cuvitru
  - Cutaquig
  - Xembify
  - Gammagard
  - Nanogam/Optiglobin
  - Clairyg
  - Tegeline
  - Pentaglobin
  - Keycute/Naxiglo
  - Gammaplex
  - Beriglobin
  - Rhesonativ
  - Rhophylac

The variables for characterisation of immunoglobulin users (*objective 4*) are as follows:

- Demographics, at index date:
  - Sex: Female/male
  - Age
  - Age group: 1 to 18 years, 19 to 65 years, >65 years and older

- Indication for use: Prespecified conditions will be used as proxies to assess the indication for immunoglobulin use, including both authorised and non-authorised indications. The assessment windows will be any time prior to 7 days after the index date [-inf, +7], 30 days prior to 7 days after the index date [-30, +7], and 7 days prior to 7 days after the index date [-7, +7].
  - Primary immunodeficiency syndrome, including:
    - Primary immunodeficiency syndromes
  - Secondary immunodeficiencies, including:
    - Secondary immunodeficiencies
  - Neurology, including:
    - Guillain Barré syndrome (GBS)
    - Chronic inflammatory demyelinating polyradiculoneuropathy (CIDP)
    - Multifocal motor neuropathy (MMN)
    - Myasthenia gravis
    - Stiff person syndrome
    - Lambert-Eaton myasthenia syndrome
  - Haematology, including:
    - Immune thrombocytopenia (ITP)
    - Acquired von Willebrand disease
    - Foetal Neonatal Alloimmune Thrombocytopenia (FNAIT)
  - Infectious diseases, including:
    - Measles
  - Solid organ transplantation, including:
    - Transplantation
  - Internal medicine, including:
    - Kawasaki's disease
    - Inflammatory myopathy
    - (Juvenile) dermatopolymyositis
    - ANCA vasculitis (replacement therapy)
    - Systemic lupus erythematosus (SLE)

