• >65	N (%)			
Sex				
• Male	N (%)			
• Female	N (%)			
Immunoglobulin brand B/C/D, etc.				
Number of subjects	N			
Number of records	N			
Cohort start date	Median			
Cohort end date	Median			
Prior observation	Median [q25 – q75]			
Future observation	Median [q25 – q75]			
Age (years)	Median [q25 – q75]			
	Min-max			
Age group (years)				
• 1 to 18	N (%)			
• 19 to 65	N (%)			
• >65	N (%)			
Sex				
• Male	N (%)			
• Female	N (%)			

\* = Interquartile ranges for cohort start and end date can be found in the Shiny app.

- Table 5. Mock table shell: Indications of use of individuals initiating immunoglobulin therapy during the study period, per immunoglobulin brand, per data source.

Indication of use	Any time prior to 7 days after index date [-inf, +7]			30 days prior to 7 days after the index date [-30, +7]			7 days prior to 7 days after the index date [-30, +7]		
	CDW Bordeaux	IQVIA DA Germany	CPRD GOLD	CDW Bordeaux	IQVIA DA Germany	CPRD GOLD	CDW Bordeaux	IQVIA DA Germany	CPRD GOLD
	n (%)	n (%)	n (%)	n (%)	n (%)	n (%)	n (%)	n (%)	n (%)
Immunoglobulin brand A									
Primary immunodeficiency syndrome									
Secondary immunodeficiencies									
Neurology									
Haematology									
Infectious diseases									
Solid organ transplantation									
Internal medicine									
Dermatology									
Hepatology									
Other indications*									
Immunoglobulin brand B/C/D, etc.									
Primary immunodeficiency syndrome									
Secondary immunodeficiencies									

Indication of use	Any time prior to 7 days after index date [-inf, +7]			30 days prior to 7 days after the index date [-30, +7]			7 days prior to 7 days after the index date [-30, +7]		
	CDW Bordeaux	IQVIA DA Germany	CPRD GOLD	CDW Bordeaux	IQVIA DA Germany	CPRD GOLD	CDW Bordeaux	IQVIA DA Germany	CPRD GOLD
	n (%)	n (%)	n (%)	n (%)	n (%)	n (%)	n (%)	n (%)	n (%)
Neurology									
Haematology									
Infectious diseases									
Solid organ transplantation									
Internal medicine									
Dermatology									
Hepatology									
Other indications*									

\* = Frequencies of 'Other indications' will be provided overall and separately for each indication, where available.

- Table 6. Mock table shell: Top 10 recorded conditions in individuals initiating immunoglobulin therapy, prior to the index date, per immunoglobulin brand, categorised by data source.

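### Section 8.8.3 dates objective 4 from the first immunoglobulin record, while Sections 8.2, 8.3 and 8.6.1 date it from the first prespecified-brand record; the 180-day follow-up exclusion has the same mismatch

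*Protocol*

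**What the plan says.** **Brand-based anchor.** Section 8.2, covering objectives 3 and 4 together, states that "follow-up of incident immunoglobulin users will start on the date of the first immunoglobulin prescription record of prespecified immunoglobulin brands during the study period". The Section 8.3 inclusion criterion for objectives 3–4 is "First drug prescription or dispensing record of prespecified immunoglobulin brand during the study period". Section 8.6.1 takes the brand record as the exposure for both objectives, and the drug-era text for objective 3 in Section 8.8.3 starts exposure at the first brand prescription.

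**Anchor without a brand restriction.** The objective 4 text in Section 8.8.3 defines the index date twice as the first recorded immunoglobulin prescription, once for the characterisation windows and once for demographics, which are "assessed at the date of first recorded prescription of immunoglobulins (index date) during the study period". The same text says results are described for each prespecified brand. The abstract's objective 4 paragraph ties the index date to immunoglobulin initiation. For hospital data the abstract says that "the study population will include all individuals who have an immunoglobulin record and are present in the data source during the study".

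**Follow-up exclusion.** Section 8.3 excludes "Individuals with a first immunoglobulin record <180 days prior to the end of data availability in the respective data source". Section 8.2 words the same rule around the first immunoglobulin record.

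**Indication windows.** Section 8.6.3 gives the narrowest window as "7 days prior to 7 days after the index date [-7, +7" (closing bracket cut off here). The third column of mock Table 5 reads "7 days prior to 7 days after the index date [-30, +7" (likewise).

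**The concern.** Within this protocol, immunoglobulin and prespecified brand are not the same set. Section 8.6.1 defines the objective 1 exposure at ingredient level. Table S3 lists those ingredients, including hepatitis B, tetanus and varicella-zoster immune globulins and monoclonals such as palivizumab. Table S4 is a separate, narrower list of brands. A programmer following Section 8.8.3 could build the objective 4 index from Table S3; one following Section 8.2 would build it from Table S4.

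The dates differ for anyone whose first immunoglobulin record in the study period is not a prespecified brand. Every objective 4 result (age, indication, infections, antibiotics) is placed relative to the index date and printed under a brand. Under the literal 8.8.3 rule, those results would describe affected people at a time before the brand record. In primary care the choice of date also affects cohort membership, because the 180-day washout counts back from it.

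**Working it through.** The protocol gives no figure to reproduce here. The check sets the two definitions side by side and uses date arithmetic.

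**Inputs.** Study period 01/01/2017 to 31/12/2024 (Section 8.5). Indication windows [-inf, +7], [-30, +7] and [-7, +7]; infection and antibiotic windows [0, +30] and [0, +365] (Section 8.6.3). Washout of 180 days for any immunoglobulin, primary care only (Section 8.3). Data end: CDW Bordeaux 09/2025, IQVIA DA Germany 12/2024, CPRD GOLD 05/2025 (Table 1).

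**1. Window displacement.** Let g be the days from the first immunoglobulin record to the first prespecified-brand record. If the index is the first immunoglobulin record, the number of days of [0, +W] that fall on or after the brand date is max(0, W + 1 − g).

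| g (days) | Days of [0, +30] on or after brand | Days of [0, +365] on or after brand | Brand date inside [-7, +7]? |
|---|---|---|---|
| 0 | 31 | 366 | yes |
| 7 | 24 | 359 | yes |
| 8 | 23 | 358 | no |
| 31 | 0 | 335 | no |
| 181 | 0 | 185 | no |
| 366 | 0 | 0 | no |

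All three indication windows close at +7, so once g is 8 or more none of them reaches the brand date. The calendar bound on g is 31/12/2024 minus 01/01/2017 = 2,921 days. With a brand-based index, g = 0 by construction and every row reverts to the first.

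**2. Who enters, in primary care.**
- g = 1 to 180: the earlier record falls inside the washout of a brand index, so the person fails. Under the 8.8.3 index the same person can enter.
- g > 180: the person can enter under either rule, with different index dates.

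CDW Bordeaux has no washout, so membership there is not affected in this way.

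**3. Follow-up exclusion.** The latest record that passes is data end minus 180 days, capped at 31/12/2024. Table 1 gives months only, so the first and last day of the month bound the result.

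| Source | Latest brand record that would pass if the rule tested the brand date | Part of study period where the anchor matters |
|---|---|---|
| IQVIA DA Germany | 04/06/2024 to 04/07/2024 | about the last six months |
| CPRD GOLD | 02/11/2024 to 02/12/2024 | the last 29 to 59 days |
| CDW Bordeaux | 31/12/2024 | none |

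For Bordeaux, 31/12/2024 plus 180 days is 29/06/2025, before data end, so no study-period record can fail under either anchor. In Germany, a person with hepatitis B immunoglobulin in 2018 and a first brand record in November 2024 would pass the literal rule with at most 60 days of data after the brand record (01/11/2024 to 31/12/2024).

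**4. Table 5.** The label of the third window says 7 days before to 7 days after, but its bracket repeats that of the second window. Section 8.6.3 and the label agree with each other; only the bracket is out of line.

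**The case against.** The best defence is that Section 8.8.3 is shorthand. Section 8.2 names objective 4 and fixes the brand anchor. Section 8.6.2 defines the objective 4 outcome among people initiating prespecified brands. Section 8.6.3 ties the infection windows to brand initiators, and the abstract ties both infections and antibiotics to them. Section 8.6.1 can also be read as requiring the brand record to be the person's first recorded prescription in the study period, which would make g zero.

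This makes a brand index the likelier intention, but it does not remove the conflict. The protocol uses the same word for the wider Table S3 class and never says that it means the brands in Section 8.8.3. No criterion enforces the 8.6.1 reading: the washout covers 180 days and primary care only.

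Some stronger inferences are tempting but not supported:
- **That objectives 3 and 4 will have different start dates.** Section 8.2 gives them one. The divergence arises only if Section 8.8.3 is programmed literally.
- **That the hospital cohort is open to any immunoglobulin user.** The abstract sentence reads that way, but Section 8.3 exempts CDW Bordeaux only from the history and washout criteria, not from the brand criterion.
- **That gaps of many years are typical.** The 2,921 days are a calendar maximum. Bordeaux patients are observed from first to last visit, and Annex II gives a median first observation period of 247 days there. That figure is not specific to immunoglobulin users, but it argues against long gaps as the usual case.
- **That the reported percentages are biased by a known amount.** The bias would be f × (p0 − p1), where f is the affected share and p0 and p1 are the proportions at the earlier date and at the brand date. The protocol gives none of the three, and even the sign is unknown.
- **That Table 5 drops the narrowest indication window.** One bracket in a mock shell is misprinted beside a correct label.

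**Conclusion.** The inconsistency is real and stands in the current text. Sections 8.2, 8.3 and 8.6.1 use the first prespecified-brand record. Section 8.8.3 Objective 4 and the 180-day exclusion use the first immunoglobulin record. Read literally, the latter rules put per-brand windows on a non-brand date, change who passes the primary care washout when the gap is 1 to 180 days, and admit people with short follow-up after the brand in IQVIA DA Germany and, marginally, CPRD GOLD.

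The effect is confined to people with an earlier non-brand immunoglobulin record in the study period. Their share is not stated, so the size of any distortion in the results cannot be given. The conclusion rests on the literal reading of Section 8.8.3; under the shorthand reading, the defect is wording that still needs correcting because the code could follow either text. The Table 5 bracket is a separate, minor misprint.

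**What to change.** - Use one brand-based index date for objectives 3–4, defined for each reported brand cohort. State whether it is the first record of that brand or the first record of any prespecified brand. The protocol leaves this open (Section 8.2 speaks of brands, Section 8.3 of a brand), and it matters for people who switch.
- Align to that definition both index-date sentences in Section 8.8.3 Objective 4, the abstract's objective 4 paragraph, and the abstract's population text for objectives 3–4, including the hospital sentence.
- Apply the 180-day follow-up exclusion in Sections 8.2 and 8.3 to the same date.
- Correct the third Table 5 bracket to [-7, +7] in both header blocks.
- Optionally, add a prespecified-brand row to the Table 2 attrition shell so the rule used is visible.

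The cost is a handful of wording edits, with no new data and no new analysis. If the analytical code already exists, also check which concept list builds the objective 4 index; a rerun is needed only if it uses the ingredient list or applies the exclusion to a non-brand record.
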